3.10. Milestones

This study is projected to begin study enrolment in April 2022 and end in June 2024. The final study report is planned to be completed in Q2 2025.

4. AMENDMENTS AND UPDATES

During feasibility to assess site interest and potential number of patients that would be enrolled in the study, it was clear that there would not be enough sites in the US willing to participate to reach our enrolment target of 250 patients. Feasibility conducted in EU sites showed that patient enrolment targets could be reached, and therefore only the EU component of the study will continue.

As only patients from EU sites will be enrolled in the study, the total enrolment decreases to 150 patients from 400 patients. The analyses of the primary and secondary objectives are descriptively only and was never intended to be pooled for US and EU patients. Therefore, removal of US patients does not change the analysis plan for the EU patients. Additionally, a precision estimate was calculated for sample sizes of 400 and 150 patients (see calculations below). The widths of 95% CI for N=400 are decreased by approximately 38% compared to the widths of 95% CI for N=150.

PRECISION ESTIMATE CALCULATION

Total Sample size	Proportion (p1)	Width (UpperCL - LowerCL)	LowerCL	UpperCL
150	0.01	0.07	0.015	0.085
	0.05	0.096	0.052	0.148
	0.1	0.0881	0.062	0.15
	0.2	0.128	0.136	0.264
	0.3	0.147	0.227	0.373
	0.4	0.157	0.322	0.478
	0.5	0.16	0.42	0.58
	0.6	0.157	0.522	0.678
	0.7	0.147	0.627	0.773
	0.8	0.128	0.736	0.864
	0.95	0.096	0.852	0.948
0.99	0.07	0.915	0.985	
400	0.01	0.0227	0.003	0.025
	0.05	0.0454	0.031	0.076
	0.1	0.0613	0.072	0.134
	0.2	0.0807	0.162	0.243
	0.3	0.0921	0.255	0.348
	0.4	0.0982	0.352	0.45
	0.5	0.1002	0.45	0.55

Total Sample size	Proportion (p1)	Width (UpperCL - LowerCL)	LowerCL	UpperCL
	0.6	0.0982	0.55	0.648
	0.7	0.0921	0.652	0.745
	0.8	0.0807	0.757	0.838
	0.9	0.0613	0.866	0.928
	0.95	0.0454	0.924	0.969
	0.99	0.0227	0.975	0.997

REVISION CHRONOLOGY

Amendment or update no	Date	Section of study protocol	Amendment or update	Reason
2 1	April 21, 2022	Sections 8.6, 8.8.1	EDC text updated.	EDC platform changed.
	April 01, 2022	Sections 5, 6, 7, 8.1., 8.2., 8.2.1., 8.2.3., 8.3.7., 8.4., 8.5., 8.7.2.2., 8.7.2.3, 8.7.2.4., 8.7.2.5., 8.9.1. 8.9.2., Table 8, Annex 3	Text regarding US sites and patients have been removed	After feasibility of patient enrolment in the US was conducted, it was clear that the enrolment target of 250 patients would not be met. As a result, a separate, retrospective study will be conducted using EHR data from the Flatiron database and the EU study will continue, unchanged.
		Sections 5, 6, 8.1., 8.2., 8.5.	The number of patients expected in the study has been reduced to 150 from 400	With a removal of the US sites, only patients in the EU will be enrolled, with an expected number of 150 patients. The analysis of the study objectives

Amendment or update no	Date	Section of study protocol	Amendment or update	Reason
				does not change despite the reduction in sample size, as all endpoints were always intended to be analyzed separately for the EU and US.
		Figure 1	The diagram showing US sites was removed	The study design figure was updated to show EU sites only
		Section 8.2.3.	The table comparing EU and US sites was removed	As US sites are no longer included in the study, the section was removed
		Section 8.9.2.	The text around retrospective data collection was specified to include the examples of the type of retrospective data that may be collected, "multiple myeloma history and treatment history"	To clarify the type of data that may be collected retrospectively
		Sections 3.4, 8.1 and 8.2	The following sentence was added, "In the event the enrolment rate after study start is too low to meet the expected 150 RRMM patients within the planned enrolment timeframe, eligible RRMM patients from sites who received their first	If there are difficulties in enrolment of patients, the option to collect retrospective data from EU sites is maintained. The additional sentence was included in Sections 3.4, 8.1 and 8.2 for clarity and consistency with the text in

Amendment or update no	Date	Section of study protocol	Amendment or update	Reason
			belantamab mafodotin dose before study enrolment will be invited for study participation.	section 8.5
		Section 3.3	Text regarding US patients has been removed from the Key Secondary objectives description in the Table	
		Table 3 and Section 8.7.2.2.	Collection of race/ethnicity data has been removed	Race/ethnicity data was largely applicable to US data. In Germany, Austria and Italy, this data cannot be collected so the decision was made to remove this data element.

5. MILESTONES

Data collection will start at the time of study enrolment of the first patient into the study in April 2022. Data will be captured prospectively for a maximum of 15 months follow-up counting from the first dose of belantamab mafodotin.

Patients treated with belantamab mafodotin for a diagnosis of RRMM usually visit the clinic every 3 weeks. Thus, data will be collected from medical charts every 3 weeks until the end of follow-up at 15 months, study discontinuation for any reason, informed consent withdrawal or death; whichever comes first.

Study end: Data collection will continue until target enrolment is achieved of approximately 150 evaluable RRMM patients as well as a maximum of 15 months of follow-up. This is expected to be achieved by June 2024.

Table 1 Detailed Study Milestones

Milestone	Planned date
Start of data collection	April 2022
End of data collection	June 2024
Registration in the EU PAS register	Q4 2021 – Q2 2022
Final report of study results	Q2 2025

6. RATIONALE AND BACKGROUND

6.1. Background

Multiple myeloma (MM) is a rare and incurable haematological malignancy which typically affects adults 60 years of age and older. It is the second most common haematological malignancy (after non-Hodgkin's lymphoma), representing 1% of all cancers and 2% of all cancer deaths. In 2020, the estimated annual, age-standardised, worldwide MM incidence rate was 1.8 per 100,000 (GLOBOCAN, 2020).

Current MM therapies include glucocorticoids (e.g., dexamethasone), chemotherapy, proteasome inhibitors (PIs, e.g., bortezomib), immunomodulatory agents (e.g., thalidomide, lenalidomide and pomalidomide), monoclonal antibodies (mAbs, e.g., daratumumab, isatuximab and elotuzumab) and the histone deacetylase inhibitor panobinostat. Since the approval of daratumumab, MM patients have emerged who are refractory to at least one PI, one immunomodulatory agent and one anti-CD38 mAb. There is a clear unmet medical need for new therapies among patients with relapsed or refractory MM (RRMM) as current treatment options are very limited with a median overall survival (OS) of approximately 7 to 10 months (Gandhi, 2019).

Belantamab mafodotin (BLENREP™) is a first in-class anti-B-cell maturation antigen therapy approved for use in the United States (US) and European Union (EU) based on data from the pivotal Phase II DREAMM-2 study (Study 205678) (Lonial, 2020; Lonial, 2021a). DREAMM-2 is a phase II, open label, randomized, two-arm study investigating the efficacy and safety of two doses of belantamab mafodotin (3.4 mg/kg vs. 2.5 mg/kg) in participants with MM who had ≥ 3 prior lines of treatment, were refractory to a proteasome inhibitor and an immunomodulatory agent and had failed an anti-CD38 antibody (Lonial, 2020; Lonial, 2021a). DREAMM-2 results after 13-month follow-up showed an overall response rate (ORR) for the 97 patients who received the registration dose (i.e., 2.5 mg/kg) of 32% (97.5% confidence interval [CI], 21.7-43.6) with 58% of responders achieving a very good partial response (VGPR) or better, including 2 stringent complete responses (sCRs) and 5 CRs (Lonial, 2021a). Median estimated duration of response (DoR), OS, and progression-free survival (PFS) were 11.0 months (95% CI, 4.2 months to not reached), 13.7 months (95% CI, 9.9 months to not reached), and 2.8 months (95% CI, 1.6-3.6 months), respectively (Lonial, 2021a). The most frequent adverse reactions ($\geq 30\%$) reported from 95 patients in DREAMM-2 who received belantamab mafodotin 2.5 mg/kg were keratopathy (71%) and thrombocytopenia (38%). The most commonly reported serious adverse reactions were pneumonia (7%), pyrexia (7%) and infusion-related reactions (3%). Permanent discontinuation due to an adverse reaction occurred in 9% of patients who received belantamab mafodotin with 3% related to ocular adverse reactions.

In the EU, belantamab mafodotin was granted a Conditional Marketing Authorisation on 25 August 2020 for the treatment of MM in adult patients who have received at least four prior therapies and whose disease is refractory to at least one PI, one immunomodulatory agent, and an anti-CD38 mAb, and who have demonstrated disease progression on the last therapy. Because of the risk of ocular toxicity, the European Medicines Agency (EMA) required additional monitoring and additional risk minimisation measures in the

form of educational materials for prescribers and patients as detailed in the Risk Management Plan (RMP) (Summary RMP, 2021). The goal of the EU RMP is to mitigate the risk of ocular toxicity of belantamab mafodotin by educating prescribers and patients. The EU Summary of Product Characteristics (SmPC) states ophthalmic examinations should be performed at baseline, before initiation of each of the subsequent 3 treatment cycles and during treatment as clinically indicated (BLENREP SmPC, 2021).

6.2. Rationale

To better understand the real-world management of RRMM patients exposed to belantamab mafodotin and the occurrence of ocular toxicity in routine clinical practice, this study aims to evaluate the real-world use, safety and effectiveness of belantamab mafodotin in 150 RRMM patients in Europe.

7. RESEARCH QUESTION AND OBJECTIVE(S)

The primary purpose of this multinational, multisite, non-interventional study is to understand the real-world use of belantamab mafodotin by characterizing RRMM patients treated with belantamab mafodotin in routine clinical practice in Europe. In addition, this study will provide further evidence on belantamab mafodotin's risk-benefit profile by collecting safety and effectiveness data. This information will be used to inform current and future clinical practice. No formal hypotheses are being tested in this study.

7.1. Primary Objective

The **primary objective** of this study is to characterize RRMM patients treated with belantamab mafodotin per routine clinical care in terms of demographics, disease status, clinical characteristics and treatment history (overall and by line of treatment).

7.2. Secondary Objectives

The **key secondary objective** of this study is to characterize patients who experience ocular adverse events (AEs) that have been associated with belantamab mafodotin treatment (ocular Adverse Events of Special Interest [AESIs]) (overall and by line of treatment) in terms of:

- Belantamab mafodotin treatment received (i.e., dose and duration)
- Ophthalmic disease history
- Ocular AESI type, duration and severity
- The frequency and timing of ophthalmic monitoring visits relative to belantamab mafodotin administration (for each cycle; overall and by line of treatment, occurrence of ocular AESIs as well as treatment dose and frequency).

Other secondary objectives are the following (overall and by line of treatment):

- Assess the incidence of ocular AESIs and their impact on treatment discontinuation, interruption/delay, or dose modifications (additionally evaluated by comorbidity, ocular AESI type and severity as well as treatment dose and frequency)
- Evaluate persistence and adherence with belantamab mafodotin
- Describe reasons for treatment discontinuation
- Describe the duration and reasons of treatment interruptions/delays, or dose modifications
- Evaluate effectiveness in terms of disease response to treatment, DoR, duration of treatment (DoT), real-world progression-free survival (rwPFS) and OS.

8. RESEARCH METHODS

8.1. Study Design

[figure not shown]
This multinational, multisite, non-interventional study will collect real-world data on the use, safety and effectiveness of belantamab mafodotin. Data will be analysed from approximately 150 RRMM patients from sites in selected countries across Europe.

Eligible RRMM patients from EU sites who are due to receive belantamab mafodotin will be consecutively invited for study enrolment by haematologists and/or oncologists affiliated with investigator sites participating in this study. In the event the enrolment rate after study start is too low to meet the expected 150 RRMM patients within the planned enrolment timeframe, eligible RRMM patients from sites who received their first belantamab mafodotin dose before study enrolment will be invited for study participation. As the study is non-interventional, the decision to treat patients with belantamab mafodotin will be made prior to and independent from the decision to enrol patients into the study, and baseline and follow-up assessments will be in accordance with local standard medical care. Investigators must refer to the SmPC (for European patients) for information on contraindications, warnings and precautions as well as use in specific populations.

Written informed consent will be obtained from all patients before enrolment into the study. Written informed consent may be obtained from family members of deceased patients, if allowed according to the regulatory and legal country-specific requirements of the participating site.

After obtaining informed consent, data will be collected retrospectively from medical records and prospectively, where applicable, from the time of the first dose of belantamab mafodotin to the end of follow-up at 15 months, study discontinuation for any reason, informed consent withdrawal or death, whichever comes first. The Investigator will follow ocular AESIs until resolved or until the last study visit of the patient.

[Figure 1](#) shows the patient and data flow in this study. For patients who will receive a first dose of belantamab mafodotin at or after study enrolment, baseline and outcome data will be entered into the electronic case report form (eCRF).

Figure 1 Patient and data flow

Abbreviations: eCRF=electronic case report form; Tx=treatment.

As shown in [Figure 1](#), eligible RRMM patients from sites who received their first belantamab mafodotin dose before study enrolment will only be invited for study participation if this is deemed necessary based on the enrolment rate in the EU.

Belantamab mafodotin use and ophthalmic monitoring data will be collected while patients are on treatment. Safety and effectiveness data will be collected regardless of whether patients are on treatment or have discontinued treatment during follow-up.

8.2. Study Population and Setting

It is planned to include approximately 150 evaluable RRMM patients from sites in selected countries across Europe who are due to receive belantamab mafodotin as part of routine clinical care after study enrolment.

Once the treatment decision has been made, independent from the decision to enrol patients into the study, eligible RRMM patients EU sites due to receive belantamab mafodotin as part of routine clinical care will be consecutively invited for prospective enrolment by health care providers affiliated with investigator sites participating in this study. Prospective data will be collected during a 15-month follow-up period from visits scheduled as part of routine clinical care. In the event the enrolment rate after study start is too low to meet the expected 150 RRMM patients within the planned enrolment timeframe, eligible RRMM patients from sites who received their first belantamab mafodotin dose before study enrolment will be invited for study participation. Available retrospective baseline and outcomes data from the time of the first belantamab mafodotin dose will be extracted from medical records. Data will be collected prospectively from study enrolment for the length of follow-up time (i.e., 15 months minus the time from the first belantamab mafodotin dose until study enrolment), if applicable. All efforts will be made to ensure that the data of retrospectively enrolled patients are of good quality and provide sufficient information.

The estimated study enrolment period is approximately 12 months for inclusion of approximately 150 eligible RRMM patients, though this may be altered based on the actual use of belantamab mafodotin during the feasibility assessment component of site initiation. It is planned to follow patients for 15 months. Belantamab mafodotin is required to be approved for use before the start of local study enrolment.

The total study duration is estimated to be a maximum of two years and three months per site based on an estimated study enrolment period of 12 months and a follow-up period of 15 months.

8.2.1. Inclusion Criteria

A patient who meets **all** of the following criteria is eligible for inclusion:

- Written informed consent
- Male or female, ≥ 18 years of age at the start of belantamab mafodotin treatment
- Confirmed diagnosis of RRMM
- Received (if deemed required for EU based on enrolment rate) or due to receive belantamab mafodotin treatment per routine clinical care by an oncologist or haematologist consistent with the approved labelling

8.2.2. Exclusion Criteria

A patient who meets **any** of the following criteria is not eligible for inclusion:

- Concurrent enrolment in an interventional clinical trial involving either an investigational medicinal product (including belantamab mafodotin) or medical device
- Concurrent enrolment in a belantamab mafodotin early access program (EAP), Named Patient Program (NPP) or temporary authorization for use (ATU) program

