3.4. Study Design

This multinational, multisite, non-interventional study aims to collect real-world data on the use, safety and effectiveness of belantamab mafodotin in RRMM patients from Europe. Background data at the time of the first dose of belantamab mafodotin (i.e., demographics, disease status, clinical characteristics and treatment history) will be collected to characterize RRMM patients treated with belantamab mafodotin per routine clinical care. In addition, data will be collected on the occurrence, duration and management of ocular AESIs, the frequency and timing of ophthalmic examinations, persistence and adherence with belantamab mafodotin, treatment discontinuations, interruptions/delays and decreased dosing, and effectiveness in terms of treatment response and survival.

Data will be analysed from approximately 150 RRMM patients from sites in selected countries in Europe. Eligible RRMM patients from EU sites who are due to receive their first dose of belantamab mafodotin will be consecutively invited for study enrolment by haematologists and/or oncologists affiliated with investigator sites participating in this study. In the event the enrolment rate after study start is too low to meet the expected 150 RRMM patients within the planned enrolment timeframe, eligible RRMM patients from sites who received their first belantamab mafodotin dose before study enrolment will be

invited for study participation.. As the study is non-interventional, the decision to treat patients with belantamab mafodotin will be made prior to and independent from the decision to enrol patients into the study, and baseline and follow-up assessments will be in accordance with local standard medical care.

After obtaining informed consent, data will be collected into an electronic case report form (eCRF) directly during prospective follow-up or will be collected retrospectively from medical records, where applicable, from the time of the first dose of belantamab mafodotin to the end of follow-up at 15 months, study discontinuation for any reason, informed consent withdrawal or death; whichever comes first. The Investigator will follow ocular AESIs until resolved or until the last study visit of the patient.

The total study duration is estimated to be a maximum of two years and three months per site based on an estimated study enrolment period of 12 months and a follow-up period of 15 months.

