3.5. Population

It is planned to include approximately 150 RRMM patients from sites in selected countries across Europe, from patients who are due to receive belantamab mafodotin as part of routine clinical care after study enrolment.

Inclusion Criteria:

A patient who meets **all** of the following criteria is eligible for inclusion:

- Written informed consent
- Male or female, ≥ 18 years of age at the start of belantamab mafodotin treatment
- Confirmed diagnosis of RRMM
- Received (first dose up to three months before study enrolment; if deemed required based on enrolment rate) or due to receive belantamab mafodotin treatment per routine clinical care by an oncologist or haematologist consistent with the approved labelling

Exclusion Criteria:

A patient who meets **any** of the following criteria is not eligible for inclusion:

- Concurrent enrolment in an interventional clinical trial involving either an investigational medicinal product (including belantamab mafodotin) or medical device
- Concurrent enrolment in a belantamab mafodotin early access program (EAP), Named Patient Program (NPP) or temporary authorization for use (ATU) program

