8.2.3. EU Setting Considerations

8.3. Variables

8.3.1. Definitions

[figure not shown]
The following definitions apply to the different timings of data collection (see [Figure 2](#)):

- **Index date** is defined as the time of the first (non-missing) dose of belantamab mafodotin.
- **The baseline period** for data collection is defined as the time from the initial MM diagnosis until the index date (the first dose of belantamab mafodotin).
- **The post-index period** spans from the index date until the end of follow-up at 15 months, study discontinuation for any reason, informed consent withdrawal or death; whichever comes first.
- **The post-index treatment period** is defined as the duration of the belantamab mafodotin line of treatment (DoT). This spans from the index date until the confirmed decision date of permanent discontinuation of belantamab mafodotin treatment, the

confirmed date of a new line of treatment or the date of the end of follow-up at 15 months, study discontinuation for any reason, informed consent withdrawal or death; whichever comes first.

- **The study period** spans from the time from the initial MM diagnosis until the end of follow-up at 15 months, study discontinuation for any reason, informed consent withdrawal or death; whichever comes first.
- **Active treatment exposure periods** are defined as the time that belantamab mafodotin is considered to have a treatment effect during the post-index treatment period. This period includes all doses occurring within 70 days of the previous dose (belantamab mafodotin's half-life) from the date of the first belantamab mafodotin dose of that sequence to the date of the last dose +70 days or the date of the end of the post-index treatment period; whichever comes first.

Figure 2 Timings of Data Collection

[figure not shown]
Abbreviations: MM=multiple myeloma.

The following definitions apply to collection of treatment data:

- **Line of treatment** is defined as one or more completed cycles of a single agent, a regimen consisting of a combination of several drugs, or a planned sequential therapy of various regimens (Rajkumar, 2015).
- **A treatment cycle** is defined as the belantamab mafodotin label-approved dosing interval, which is 21 days (with a real-world scheduling grace period of +7 days).
- **Treatment discontinuation** is defined as a recorded clinician decision (with an associated decision date) to permanently discontinue belantamab mafodotin treatment.

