8.5. Study Size

Approximately 150 evaluable RRMM patients are planned for the study. The sample size is not based on statistical power consideration but on a conservative estimate for each country of interest based on country-specific MM incidence and prevalence rates, the percentage of patients expected to be eligible for belantamab mafodotin treatment, the expected belantamab mafodotin market uptake, site availability and the treatment landscape in terms of ongoing clinical trials.

The sample size 150 RRMM patients from EU sites is considered sufficient to meet the primary objective of describing RRMM patients treated with belantamab mafodotin per

routine clinical care in terms of demographics, disease status, clinical characteristics and treatment history.

To meet the planned number of 150 evaluable RRMM patients, the enrolment period may be extended if needed based on the actual uptake of belantamab mafodotin and site participation. Eligible RRMM patients from sites who received their first belantamab mafodotin dose before study enrolment will be invited for study participation if this is deemed necessary based on the enrolment rate in the EU. The number of patients who received their first belantamab mafodotin dose before study enrolment is expected to be low as belantamab mafodotin was either only recently launched or is in the process of being launched.

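### The operative eligibility criteria do not carry the protocol's own first-dose design, so patients previously exposed to belantamab mafodotin can qualify

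*Protocol*

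**What the plan says.** **Abstract.** Section 3.4 says that patients "who are due to receive their first dose of belantamab mafodotin will be consecutively invited". The inclusion criterion in section 3.5 reads "Received (first dose up to three months before study enrolment; if deemed required based on enrolment rate) or due to receive belantamab mafodotin treatment". Section 3.7 repeats the three-month limit for patients whose data are collected retrospectively.

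**Main text.** Section 8.2.1 has "Received (if deemed required for EU based on enrolment rate) or due to receive belantamab mafodotin treatment per routine clinical care", with no mention of a first dose and no look-back limit. The recruitment sentences in 8.1 and 8.2 also lack the first-dose wording for patients about to be treated. Both sections do describe a second group, whose first dose came before enrolment and who are invited only if accrual is too slow, but they set no limit on how long before.

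**Exclusions.** Section 8.2.2 lists two. One is "Concurrent enrolment in a belantamab mafodotin early access program (EAP), Named Patient Program (NPP) or temporary authorization for use (ATU) program". The other is "Concurrent enrolment in an interventional clinical trial involving either an investigational medicinal product (including belantamab mafodotin) or medical device". Section 3.5 has the same pair. Neither mentions past participation.

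**Index date.** Section 8.3.1 has it "defined as the time of the first (non-missing) dose of belantamab mafodotin". OS and rwPFS in the same section run from the start of belantamab mafodotin treatment.

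**The concern.** Sites screen against the criteria in 8.2.1 and 8.2.2. If those criteria are wider than the stated design, the cohort can include patients the design does not intend.

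The patient in question took belantamab mafodotin in a trial or access programme, has left it, and is now due to receive the drug in routine care. Three sets of results are exposed:

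- **Primary objective (8.7.2.2).** Visual acuity and slit-lamp findings before or at index are reported as baseline characteristics. In a previously exposed patient they may be partly effects of the drug.
- **Key secondary objective (8.7.2.3).** Time to first ocular AESI means little if an earlier event occurred before the recorded start.
- **Other secondary objectives (8.7.2.4).** First-event incidence, persistence at 3 to 15 months, rwPFS and OS would combine patients starting the drug with patients who had already tolerated it for some time.

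**Working it through.** The protocol gives no figure that depends on this wording, so the main check is a comparison of text.

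**Step 1: where each restriction appears**

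| Restriction | Abstract | Main text |
|---|---|---|
| Patients about to be treated are due their first dose | Stated in 3.4; not in the 3.5 criterion | Absent from the recruitment sentences of 8.1 and 8.2 and from 8.2.1 |
| Earlier first dose at most three months before enrolment | 3.5 and 3.7 | Absent from 8.1, 8.2 and 8.2.1 |
| Prior access-programme exposure excluded | Not stated (3.5: concurrent only) | Not stated (8.2.2: concurrent only) |
| Prior trial exposure excluded | Not stated (3.5: concurrent only) | Not stated (8.2.2: concurrent only) |

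**Step 2: apply the main-text criteria to one patient.** Take an adult with RRMM who consents, has completed an access programme, and is about to be given commercial drug consistent with the label. The patient is "due to receive belantamab mafodotin treatment per routine clinical care by an oncologist or haematologist consistent with the approved labelling" and is not concurrently enrolled in anything. Every bullet in 8.2.1 is met and no bullet in 8.2.2 applies.

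**Step 3: the index date under two readings.**
- *First-ever dose (the literal reading).* The clock is right, but without the three-month limit the index date can lie far back. Section 8.2 gives prospective follow-up as 15 months minus the time from first dose to enrolment. With the limit, at least 15 − 3 = 12 months remain. Without it, the remainder can be zero: from the conditional authorisation (August 2020) to the start of data collection (April 2022) is 20 months, which is more than 15.
- *First recorded dose.* The qualifier (non-missing) permits this where earlier doses are not captured. The clock then starts partway through treatment.

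**Step 4: illustration of size.** The share of previously exposed patients is not given, so the shares below are assumptions. Inputs from section 6.1: keratopathy 71%, median PFS 2.8 months, median DoR 11.0 months. N = 150 from section 8.5.

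Carried-over keratopathy = 150 × share × 0.71:

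| Assumed share | Patients | With prior keratopathy |
|---|---|---|
| 2% | 3 | 2.1 |
| 5% | 7.5 | 5.3 |
| 10% | 15 | 10.7 |
| 20% | 30 | 21.3 |

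These are upper-end counts, because 71% is a cumulative trial rate and not the prevalence at a later restart.

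Progression-free at 6 months, assuming exponential times and that every carried-over patient is an ongoing responder:
- new starters: 0.5^(6/2.8) = 0.226
- carried-over responders: 0.5^(6/11.0) = 0.685
- difference: 0.685 − 0.226 = 0.459
- shift in the cohort figure: 0.459 × 0.05 = 0.023; × 0.10 = 0.046; × 0.20 = 0.092

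That is about 2, 5 and 9 percentage points. It shows the direction and rough scale under favourable assumptions; it is not an estimate.

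**The case against.** The case against a serious defect is substantial.

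- **The protocol sorts patients by date of first dose.** Sections 8.1, 8.2 and 8.5 separate those dosed at or after enrolment from those dosed before it, and invite the second group only if accrual is low. On that reading a former programme patient is not a new starter. This stands as a statement of intent. But it governs when such patients are invited, not whether they are eligible, and once the provision is used 8.2.1 sets no limit.
- **The three-month limit would catch many of them.** Section 3.7 states it without regard to the source of supply. That is correct, but the limit is missing from the main-text criteria.
- **The index date is sound as written.** A reader might infer that it is misplaced by definition. The text does not support that: first dose, taken literally, means first-ever dose. Misplacement needs earlier doses to go unrecorded.
- **Few patients are expected.** A reader might take launch timing as evidence of many patients moving over from access programmes. Section 8.5 argues the opposite: it gives as the reason for expecting few earlier first doses that "belantamab mafodotin was either only recently launched or is in the process of being launched".
- **Carried-over patients need not be responders.** Treatment must be consistent with the label, and the indication quoted in section 6.1 requires progression on the last therapy. An ongoing responder counted as a new start would not fit, and a re-treated patient need not be a responder. This removes any claim to a derived effect size.
- **Carry-over may be visible.** Prior therapies with dates, eye history and baseline eye findings are collected (8.3.2). Flagging such patients is a matter for the SAP. Who may enter is a matter for the protocol.

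**Conclusion.** The point holds as a mismatch between the stated design and the operative criteria. The design is first-dose; the main-text criteria do not require a first dose, omit the three-month limit, and exclude only concurrent trial or programme enrolment. A previously exposed patient can therefore meet every listed criterion.

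The consequences are possible, not demonstrated. Baseline eye findings could be partly drug effects, and the time-to-event and persistence results could mix new and prevalent users. How many patients this concerns cannot be derived from the protocol, which expects few with an earlier first dose. The shifts of 2 to 9 points and the keratopathy counts rest on assumed shares of 2% to 20%; the shifts also rest on exponential times and on every carried-over patient being an ongoing responder. A reader might infer from them that persistence, rwPFS and OS will be inflated; the documents support only that they could be.

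The correction is still worth making. It is specific, it reduces prevalent-user and survivor bias, and eligibility is fixed in the protocol.

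**What to change.** 1. In 8.1, 8.2 and 8.2.1, use one wording that matches 3.4 and 3.5: *received (first dose up to three months before enrolment, if required by the enrolment rate) or due to receive their first dose of belantamab mafodotin*. Add the first-dose wording to the second half of the 3.5 criterion as well.
2. In 3.5 and 8.2.2, change the belantamab access-programme exclusion from concurrent to *prior or concurrent*, and add prior receipt of belantamab mafodotin in a clinical trial.
3. In 8.3.1, define the index date as the date of the first-ever dose from any source, without the (non-missing) qualifier.

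A rule making patients ineligible when the first-dose date is unknown is not needed and would add a selection step of its own.

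The cost is a few words in the criteria, one eligibility question in the eCRF, and the loss of a few patients moving from access programmes or trials to routine supply, which may slow accrual slightly.
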